7.8.1.6 Events qualifying for external adjudication by the Clinical Event Committee (CEC)

For DKA events see Section 7.8.1.12.

7.8.1.7 Other AEs

Not applicable for this trial.

7.8.1.8 Pancreatic Events Qualifying for External Adjudication by the CEC

Not applicable for this trial.

7.8.1.9 AEs while patients taking wrong medication

A listing will be provided for AEs that occurred while a patient was taking the wrong medication.

7.8.1.10 Adjudicated Hepatic Injury Events

The assessments will be analysed on project level.

7.8.1.11 Adjudicated Cancer Events

The assessments will be analysed on project level.

7.8.1.12 Adjudicated DKA Events

The assessments will be analysed on project level.

7.8.2 Laboratory data

For continuous safety laboratory parameters, standardised and normalised values will be derived as well as the differences to baseline. The process of standardisation and normalisation as well as standard analyses for safety laboratory data are described in the BI

guidance for the Display and Analysis of Laboratory Data (8). All analyses considering multiple of times ULN will be based on original and not normalised data.

To support analyses of liver related adverse drug effects, patients with aspartate transaminase (AST) and/or alanine transaminase (ALT) $\geq 3 \times \text{ULN}$ with concomitant or subsequent total bilirubin (TBL) $\geq 2 \times \text{ULN}$ in a 30 day period after AST/ALT elevation are of importance. The start of the 30 day time span is triggered by each liver enzyme elevation above the defined thresholds. If the 30 day period for TBL spans both treatment periods, the event is assigned based on the date of AST/ALT elevation. Patients who fulfil one or two of the criteria for AST/ALT or TBL elevations above and have no information available for the remaining parameter(s) at the same time-point or within the 30 day time window will not be listed under "ALT and/or AST $\geq 3 \times \text{ULN}$ with TBL $\geq 2 \times \text{ULN}$ ". An additional presentation including all events up to 30 days after the last dose of study treatment will also be included.

All calculations for the grading of renal function will be based on the originally measured laboratory values and the ULNs given by the laboratory, not on normalised values with BI standard reference ranges. The creatinine clearance and glomerular filtration rate will be estimated according to the two formulas and stored in the trial databases:

- Cockcroft-Gault formula (mL/min): $e\text{CCr} = (140 - \text{age}) \times (\text{weight in kg}) \times (0.85 \text{ if female}) / (72 \times \text{creatinine (mg/dL)})$
 - Black female:
 - If serum creatinine ≤ 0.7
CKD-EPI formula (mL/min/1.73m²): $e\text{GFR (mL/min/1.73m}^2) = 166 \times [\text{serum creatinine (mg/dL)/0.7}]^{-0.329} \times 0.993^{\text{age}}$
 - If serum creatinine > 0.7
CKD-EPI formula (mL/min/1.73m²): $e\text{GFR (mL/min/1.73m}^2) = 166 \times [\text{serum creatinine (mg/dL)/0.7}]^{-1.209} \times 0.993^{\text{age}}$
 - Black male:
 - If serum creatinine ≤ 0.9
CKD-EPI formula (mL/min/1.73m²): $e\text{GFR (mL/min/1.73m}^2) = 163 \times [\text{serum creatinine (mg/dL)/0.9}]^{-0.411} \times 0.993^{\text{age}}$
 - If serum creatinine > 0.9
CKD-EPI formula (mL/min/1.73m²): $e\text{GFR (mL/min/1.73m}^2) = 163 \times [\text{serum creatinine (mg/dL)/0.9}]^{-1.209} \times 0.993^{\text{age}}$

Age will be considered as a discrete variable for the above calculations, and the age will be from the same visit as the other variables. If a value is not available, an interpolated value from the previous and subsequent visits will be used. If no subsequent value is available an LOCF approach will be used. Baseline values will not be interpolated and no interpolation will be done across study periods. See [Section 6.6](#) for further information.

For the analysis of eGFR (CKD-EPI) and for the covariates in the statistical modelling the values calculated from the above formula using the serum creatinine values from the central

laboratory will be used, not the eGFR values provided by the central laboratory. For the assignment of PVs based on renal function the central laboratory values will be used.

Table 7.8.2: 1 CKD-EPI staging

Stage	eGFR (CKD-EPI) (mL/min/1.73m ²)	Description	Label for displays	Additional labels#
1	≥120	Normal renal function	≥120 (normal)	≥120 (normal)
2	<120 to >60	Mild renal impairment	<120 to >60 (mild)	<120 to >60 (mild)
3	≤60	Moderate/severe or end-stage renal impairment	≤60 (moderate/severe)	≤60 (moderate/severe)

Staging of the eCCr will be prepared with respect to the following categorisation and a shift table will be supplied for eCCr as well (Table 7.8.2: 2)

Table 7.8.2: 2 Cockcroft-Gault eCCr staging

Stage	eCCr (mL/min)	Description	Label for displays
1	≥90	Normal renal function	≥90 (normal)
2	60 to <90	Mild renal impairment	60 to <90 (mild)
3	30 to <60	Moderate renal impairment	30 to <60 (moderate)
4	<30	Severe renal impairment and beyond (e.g. End-stage renal disease)	15 to <30 (severe) + <15 (end-stage): <30 (severe to end stage)

The analyses of laboratory data will be descriptive in nature and will be based on BI standards (see DM&SM: Display and Analysis of Laboratory Data) [\(8\)](#).

Baseline for safety laboratory parameters will be the last available measurement before the start of randomised trial drug. Laboratory measurements taken up to 3 days after the last administration of randomised trial drug will be considered as on-treatment or up to start of treatment with a new trial drug in the extension trial, whichever comes first.

Laboratory values will be compared to their reference ranges and frequency tables will be provided for the number of patients within and outside the reference range at baseline and the last measurement on-treatment. Descriptive statistics will be provided by treatment group for baseline, on-treatment values and for changes from baseline. Frequency tables will summarise the number of patients with potentially clinically significant abnormalities as defined for the new XLAB macro (version 2.03). Details on patients with elevated liver enzymes will be listed. Summaries will also be presented for patients with elevated liver

enzymes. A scatter plot of peak ALT against peak TBL will be presented with reference lines for 3xULN and 2xULN TBL, including an indicator for treatment received.

A summary will also be created representing the number of patients per treatment group that experienced a doubling in creatinine on-treatment compared to baseline that was out of the normal range.

Only patients with at least one available on-treatment value will be included in the analysis of an individual laboratory parameter. All individual data will be presented in listings.

Urine creatinine does not have a reference range and is determined to calculate the albumin / creatinine ratio. Only the albumin / creatinine ratio will be analysed as for urine creatinine no normalised values can be derived. In cases where urine albumin values are reported to be below the quantification limits (e.g. <3 mg/L) the albumin / creatinine ratio is determined as missing and will not be replaced by estimated values. Additional summaries will be presented for the descriptive statistics of urine albumin/creatinine ratio by baseline value: normal (<30mg/g), microalbuminuria (30-≤300 mg/g) and macroalbuminuria (>300 mg/g), urine albumin by baseline value (<20mg/L, 20-<200mg/L and ≥200mg/L) and transitions from baseline based on the aforementioned categories.

A shift table from baseline to last value on-treatment for eGFR (CKD-EPI) will be provided in Section 15 of the CTR and eCCr (Cockcroft-Gault) will be provided in Appendix 16.1.9.2 of the CTR.

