3.3.3 Exclusion criteria

1. Uncontrolled hyperglycemia with a glucose level >270 mg/dl (>15.0 mmol/L) after an overnight fast during placebo run-in (includes Visit 2.1) and confirmed by a second measurement (not on the same day).
2. Exposure to any other antidiabetic medication within 12 weeks prior to randomisation other than metformin, sulfonylurea, DPP-4 inhibitor, metformin plus sulfonylurea or metformin plus DPP-4 inhibitor.
3. Current hypertension treatment with oral Minoxidil (topical minoxidil for hair growth is allowed).
4. Mean seated SBP ≥ 181 mmHg during placebo run-in visit and confirmed by a second measurement (not on the same day) preferably within one day.
5. Upper arm circumference that exceeds the upper circumference level of the cuff size of either ABPM and/or BP measurement device used in the study.
6. Night shift workers who routinely sleep during the daytime and/or whose work hours include midnight.
7. Diagnosis of autoimmune diabetes/Type I diabetes mellitus, monogenic (neonatal or maturity onset diabetes of the young (MODY)) diabetes or Type I diabetes in adults/latent autoimmune diabetes of adults (LADA) per investigator or patient medical history at the time of Visit 1 (screening).
8. Known or suspected secondary hypertension (e.g. renal artery stenosis, pheochromocytoma, Cushing's disease).

Proprietary confidential information.

© 2016 Boehringer Ingelheim International GmbH or one or more of its affiliated companies. All rights reserved.

This document may not - in full or in part - be passed on, reproduced, published or otherwise used without prior written permission.

9. History or evidence of hypertensive retinopathy (Keith-Wagener grade III or IV) and/or hypertensive encephalopathy.
10. Clinically significant valvular heart disease or severe aortic stenosis in the opinion of the investigator.
11. Acute coronary syndrome (non- ST wave elevated myocardial infarction (STEMI), STEMI and unstable angina pectoris), stroke or transient ischemic attack within 3 months prior to informed consent.
12. Indication of liver disease, defined by serum levels of either ALT (SGPT), AST (SGOT), or alkaline phosphatase above 3 x upper limit of normal (ULN) as determined during screening and/or run-in phase.
13. Impaired renal function, defined as eGFR < 45 ml/min/1.73m² (moderate renal impairment, chronic kidney disease epidemiology collaboration CKD-EPI formula) as determined during screening and/or run-in phase.

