Proprietary confidential information.

© 2016 Boehringer Ingelheim International GmbH or one or more of its affiliated companies. All rights reserved.

This document may not - in full or in part - be passed on, reproduced, published or otherwise used without prior written permission.

Renal function impairment will be classified in the following way:

- eGFR \geq 120 ml/min/1.73m²;
- eGFR 120-60 ml/min/1.73m²;
- eGFR \leq 60 ml/min/1.73m²

These 3 classes of renal impairment will be the basis for stratification at randomisation

Empagliflozin influences hepatic glucose output and hepatic triglyceride mobilization which could theoretically reduce fat stores in the liver. This may improve liver function and reduce the burden of NAFLD. NAFLD fibrosis score will be used to assess changes in the status of NAFLD.

NAFLD fibrosis score will be calculated in-house:

$$\text{NAFLD Fibrosis Score} = -1.675 + 0.037 \times \text{age (yr)} + 0.094 \times \text{BMI (kg/m}^2\text{)} + 1.13 \times \text{IFG/diabetes mellitus (yes = 1, no = 0)} + 0.99 \times \text{AST/ALT ratio} - 0.013 \times \text{platelet (x10}^9\text{/L)} - 0.66 \times \text{albumin (g/dl)}$$

Pregnancy testing (urine) will be performed in female patients of child-bearing potential only according to the time points indicated in the [Flow Chart](#).

Criteria for hypoglycaemic events

Every episode of plasma glucose \leq 70 mg/dl (3.9 mmol/l) should be documented in the eCRF with the respective time and date of occurrence. Any hypoglycemia with glucose values $<$ 54 mg/dl ($<$ 3.0 mmol/l) and all symptomatic and severe hypoglycemias should be documented as an AE "hypoglycaemic event".

For the analysis, all hypoglycemias will be classified according to the following criteria:

- Asymptomatic hypoglycemia: Event not accompanied by typical symptoms of hypoglycemia but with a measured plasma glucose concentration \leq 70 mg/dl (3.9 mmol/l)
- Documented symptomatic hypoglycemia with glucose concentration \geq 54 mg/dl and \leq 70 mg/dl (\geq 3.0 mmol/l and \leq 3.9 mmol/l): Event accompanied by typical symptoms of hypoglycemia
- Documented symptomatic hypoglycemia with glucose concentration $<$ 54 mg/dl ($<$ 3.0 mmol/l): Event accompanied by typical symptoms of hypoglycemia but no need for external assistance
- Severe hypoglycaemic episode: Event requiring the assistance of another person to actively administer carbohydrate, glucagon or other resuscitative actions.

Proprietary confidential information.

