Summaries of hypoglycaemic events will include total number of hypoglycaemic events, descriptive hypoglycaemic event rate, number of episodes per patient, severity and intensity of the worst episode, action taken, minimum glucose level of worst episode, and time to onset of first episode. Hypoglycaemic events will also be summarised by baseline eGFR category (CKD-EPI) and age group.

In addition, the frequency of hypoglycaemic AEs characterized by the latest BICMQ version terms will also be produced.

Different tables will be shown for (i) patients with investigator defined asymptomatic or symptomatic hypoglycaemia reported as AE or non-AE, (ii) patients with confirmed hypoglycaemic AEs, i.e. hypoglycaemic AEs that had a plasma glucose concentration ≤ 3.9 mmol/L (≤ 70 mg/dL) or required assistance, and, (iii) patients with minor, confirmed hypoglycaemic AEs, defined as a hypoglycaemic event that had a plasma glucose concentration ≤ 3.9 mmol/L (≤ 70 mg/dL) but did not require assistance.

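### The SAP's three-class eGFR staging conflicts with its own eCCr staging and, if used for the main eGFR shift table, cannot show worsening in patients who enter at eGFR 45 to 60

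*SAP*

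**What the plan says.** **Origin of the classes.** Protocol 5.2.3 classifies renal function impairment by eGFR as at least 120, 120 to 60, and at most 60 ml/min/1.73m². It adds: "These 3 classes of renal impairment will be the basis for stratification at randomisation". The same classes appear as strata in Protocol 7.1 and 7.5.

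**eGFR staging.** SAP 7.8.2, Table 7.8.2: 1, takes over these cut-points and attaches clinical words and display labels. Stage 1 (120 or more) is normal. Stage 2 is "<120 to >60 Mild" renal impairment. Stage 3 (60 or below) is "Moderate/severe or end-stage renal impairment", with no lower subdivision.

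**eCCr staging.** Table 7.8.2: 2 directly below has four stages: normal at 90 or more, mild from 60 to below 90, "30 to <60 Moderate", and severe to end-stage below 30. It is introduced with: "Staging of the eCCr will be prepared with respect to the following categorisation and a shift table will be supplied for eCCr as well".

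**Where the tables are reported.** SAP 7.8.2 states: "A shift table from baseline to last value on-treatment for eGFR (CKD-EPI) will be provided in Section 15 of the CTR". The eCCr shift table goes to Appendix 16.1.9.2.

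**Who can enter.** Protocol exclusion criterion 13 reads "Impaired renal function, defined as eGFR < 45" ml/min/1.73m², so patients from 45 upwards are eligible.

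**The concern.** Protocol 1.2 reports a reduction in GFR on empagliflozin that gradually returned toward baseline. A decline in eGFR is therefore a foreseeable finding, and the shift table is where a reader would look for patients who moved to a worse category.

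There are two difficulties. First, the same words carry different cut-points in adjacent tables, so the trial report could describe one patient's kidneys in two ways from one sample. Second, the eGFR staging has a floor at 60 while the trial admits patients down to 45. The patients with the least renal reserve start in the bottom class, where a deterioration of any size counts as no change.

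**Working it through.** The plan states no figure to reproduce. The check applies the SAP's own formulas and cut-points.

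**Inputs**
- CKD-EPI, black male, creatinine above 0.9 mg/dL (SAP 7.8.2): eGFR = 163 × (Scr/0.9)^-1.209 × 0.993^age. For black females above 0.7 mg/dL, 166 and 0.7 replace 163 and 0.9.
- Cockcroft-Gault (SAP 7.8.2): eCCr = (140 − age) × weight / (72 × Scr), times 0.85 if female.
- eGFR cut-points 120 and 60; eCCr cut-points 90, 60 and 30.
- Doubling summary (SAP 7.8.2): creatinine doubled from baseline and out of the normal range. AESI laboratory criterion (Protocol 5.2.2.1, SAP 7.8.1.5): at least a 2-fold rise and above the upper limit of normal.

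**1. One sample, two labels.** Take a man aged 55 with creatinine 1.0 mg/dL.
- eGFR = 163 × (1.0/0.9)^-1.209 × 0.993^55 = 97.5, labelled mild.
- eCCr at an assumed 80 kg = 85 × 80/72 = 94.4; at an assumed 110 kg = 85 × 110/72 = 129.9. Both are labelled normal.

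**2. The floor.** Under Table 7.8.2: 1, the values 60, 58, 45, 29 and 25 are all stage 3. Any fall from a baseline of 45 to 60 is stage 3 to stage 3. A fall from 119 to 61 likewise stays in stage 2.

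**3. What the doubling rule catches.** At eGFR 60 or below, creatinine is on the −1.209 branch at any realistic age. At a fixed age, the creatinine ratio for a fall from a to b is therefore (a/b)^(1/1.209), for either sex.

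| eGFR change | Creatinine ratio | eGFR stage change | Doubling met |
|---|---|---|---|
| 58 to 25 | 2.006 | none | yes, just |
| 58 to 26 | 1.94 | none | no |
| 58 to 29 | 1.77 | none | no |
| 45 to 29 | 1.44 | none | no |

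Doubling multiplies eGFR by 2^-1.209 = 0.4326. A patient starting at 60 must reach about 26.0, one at 58 about 25.1 and one at 45 about 19.5. Falls that stop above those values miss the eGFR shift table, the doubling summary and the AESI laboratory criterion together.

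**4. What the appendix eCCr table adds.** Take a man aged 60. Inverting CKD-EPI gives creatinine 1.493 mg/dL at eGFR 58, 1.842 at 45 and 2.649 at 29. Then eCCr = 80 × weight/(72 × Scr):

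| Assumed weight | 58 to 29 | 45 to 29 |
|---|---|---|
| 70 kg | 52.1 to 29.4, moderate to severe | 42.2 to 29.4, moderate to severe |
| 80 kg | 59.5 to 33.6, no shift | 48.3 to 33.6, no shift |
| 95 kg | 70.7 to 39.9, mild to moderate | 57.3 to 39.9, no shift |
| 110 kg | 81.9 to 46.1, mild to moderate | 66.4 to 46.1, mild to moderate |

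The eCCr table picks up some of these falls, depending on weight, but not all.

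**5. After the change.** With 90/60/30 applied to eGFR, both 58 to 29 and 45 to 29 become moderate to severe. A fall from 58 to 40 (1.36-fold) still shows no shift unless the class is also split at 45.

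**The case against.** The case on the other side has real force in several places.

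- **The SAP did not invent the classes.** Protocol 5.2.3 presents them as its classification of renal impairment. This stands: the SAP adds the normal, mild and moderate/severe wording, and any restaging should be recorded as a departure from that protocol text.
- **A reader might infer that patients at eGFR 90 to 120 are normal and are mislabelled.** The documents do not establish this. They give no other normal limit for eGFR, and the limit of 90 belongs to a different measure, which depends on weight and is not indexed to body surface area. What they do establish is that the two tables use the same words inconsistently.
- **A reader might infer that a fall from 58 to 25 would go unseen.** It would not. It is a 2.006-fold creatinine rise, so the doubling summary and the AESI criterion would catch it, provided creatinine is above the normal range. The gap concerns falls short of doubling.
- **A reader might infer that the hypoglycaemia summary certainly uses this staging.** SAP 7.8.1.4 says "Hypoglycaemic events will also be summarised by baseline eGFR category (CKD-EPI) and age group" without giving the categories. SAP 7.1 refers category definitions to Section 6.4, which is not in the public text.
- **Other outputs remain.** SAP 7.8.2 and 7.8.5.1 plan changes from baseline, creatinine and eGFR over time with plots, counts of potentially clinically significant abnormalities (by criteria the documents do not give) and individual listings. SAP 7.8.1.5 adds an acute renal failure adverse event table. These limit the loss, but none of them is specified as a count of patients crossing an eGFR threshold.

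**Conclusion.** The point holds as a low-cost defect in descriptive safety reporting. That the labels of the two staging tables conflict is plain from the text. The floor effect is arithmetic, but it is conditional: it assumes that the Section 15 eGFR shift table uses Table 7.8.2: 1. That is a reasonable inference from the display-label column and from the eCCr shift table being described as supplied in addition, but the SAP does not state it.

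On that assumption, no patient entering at eGFR 45 to 60 can show a worsening in the table. Falls to above about 26.0 (from 60) or 19.5 (from 45) also miss the doubling summary and the AESI laboratory criterion. The documents do not say how many patients will enter at 45 to 60, so the size in patients is unknown. Safety analyses are descriptive, and the primary and key secondary tests are not affected.

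**What to change.** 1. Keep the 120/60 classes for stratification and as the model covariate. Label them as strata, without impairment wording.
2. For the eGFR shift table, use the cut-points already in Table 7.8.2: 2 (90 or more, 60 to below 90, 30 to below 60, below 30), and name them in the sentence that announces the table. A further split at 45, the eligibility limit, is optional.
3. State the categories for the safety summaries by eGFR. If they use Table 7.8.2: 1, apply the same change.
4. Record in SAP Section 4 that this display departs from the classification in Protocol 5.2.3.

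The cost is one recoding of a variable already derived. A four-class shift table has 16 cells per arm instead of 9, for a planned 77 patients per arm, so cells will be sparser. No new data are needed, and randomisation and the confirmatory models are unchanged.

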5.2.2.2 Adverse event and serious adverse event collection and reporting

AE Collection

The Investigator shall maintain and keep detailed records of all AEs in their patient files. The following must be collected and documented on the appropriate eCRF by the Investigator:

From signing the informed consent onwards through the Residual Effect Period (REP) until trial completion (individual patient's End of Trial):

- all AEs (serious and non-serious), and AESIs. This also applies to patients who prematurely discontinue from the study.

If an individual patient discontinues trial medication prematurely but stays in the trial (i.e. if further visits incl. telephone visits, or vital status assessments are planned) from then on and until the individual patient's End of Trial contact, the Investigator must report all AEs (serious and non-serious) and AESIs.

[figure not shown]
After the individual patient's end of trial:

Proprietary confidential information.

© 2016 Boehringer Ingelheim International GmbH or one or more of its affiliated companies. All rights reserved.

This document may not - in full or in part - be passed on, reproduced, published or otherwise used without prior written permission.

- The Investigator does not need to actively monitor the patient for AEs but should only report relevant SAEs and relevant AESIs of which the Investigator may become aware of.

The REP is defined as ≤ 7 days following last intake of trial medication. All AEs which occurred through the treatment phase and throughout the REP will be considered as on treatment please see [Section 7.3.3](#). Events which occurred after the REP will be considered as post treatment events.

AE Reporting to Sponsor and Timelines

The Investigator must report SAEs, AESIs, and non-serious AEs which are relevant for the reported SAE or AESI, on the BI SAE form via fax immediately (within 24 hours) to the Sponsor's unique entry point (country specific contact details will be provided in the ISF). The same timeline applies if follow-up information becomes available. In specific occasions the Investigator could inform the Sponsor upfront via telephone. This does not replace the requirement to complete and fax the BI SAE form.

With receipt of any further information to these events, a follow-up SAE form has to be provided. For follow-up information the same rules and timeline apply as for initial information.

Information required

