6.2.3 End of trial and follow-up period

For all patients who successfully complete the study according to the protocol a follow-up visit (Visit 8) with the patient should be done by the investigator at the end of the follow-up period of 14 days.

Visit 8 (follow-up visit)

- Vital signs
- Body weight measurement
- BP measurement and orthostatic blood pressure test should always be done before taking any blood samples.
- Collection of urine and blood for laboratory testing.
- Home blood glucose monitoring
- Documentation of any adverse events.
- Documentation of concomitant therapies

Patients discontinuing trial medication early from the trial

In general patients should be encouraged to re-start study medication in case of temporary treatment interruptions. If the duration of interruption is more than 7 days, this should be recorded in the "Study Medication Temporary Discontinued/re-started" eCRF.

For the analysis of this trial it is absolutely crucial that all planned assessments are done as planned, even if patients discontinue trial treatment. Patients who discontinue treatment prematurely and who do not withdraw their informed consent must therefore be followed up for the intended regular treatment period. All assessments related to the primary and secondary endpoints must be performed as if the patient would have remained on treatment.

Proprietary confidential information.

© 2016 Boehringer Ingelheim International GmbH or one or more of its affiliated companies. All rights reserved.

This document may not - in full or in part - be passed on, reproduced, published or otherwise used without prior written permission.

For patients who stop study medication permanently prior to completion of 24 weeks of treatment and who are willing to be followed up, the following should be performed whenever possible:

- Premature treatment discontinuation (PTD) visit should be performed within 7 days of last intake of study drug or as soon as possible including all examinations and assessments that are part of the Visit 7.2. If the PTD visit occurs within the time window of a scheduled visit, the PTD visit will replace the scheduled visit.
- Subsequently, a follow-up visit (Visit 8 procedures) should be conducted within 14 days of the PTD visit that replaces the next visit according to the visit schedule.
- Thereafter, patients would be followed up according to the visit schedule.

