- Visit 7.2 will be the last visit for these patients. Follow-up Visit 8 does not need to be performed.

The last per study contact should be at Visit 7.2. If determined by investigator as necessary for patient safety, new antidiabetic medication regimen can be started immediately after discontinuation and must be recorded in eCRFs.

If a patient is not able to attend a study visit, the study staff should contact him/her (or someone designated – e.g. family member or personal physician) to inquire about medical information pertaining to adverse events, particularly primary and key secondary outcome events, and/or mortality, until the end of the study. Alternatively, data should be collected from medical records.

For patients who discontinue treatment prematurely but do not wish to follow the visit schedule, the following should be performed whenever possible:

- Visit 7.2 should be performed within 7 days of last intake of study drug.
- Subsequently, a follow-up visit (Visit 8 procedures) should be conducted within 14 days of the premature discontinuation visit.

If this patient withdraws consent, then the last per study contact will be Visit 8.

Patients who withdraw consent

Patients who withdraw consent during the trial should perform Visit 7.2 within 7 days of last intake of study drug. A follow-up visit (Visit 8 procedures) should be conducted within 14 days of the premature discontinuation for their safety.

The following procedures should be performed at Visit 8.

- Vital signs

Proprietary confidential information.

© 2016 Boehringer Ingelheim International GmbH or one or more of its affiliated companies. All rights reserved.

This document may not - in full or in part - be passed on, reproduced, published or otherwise used without prior written permission.

- Body weight measurement
- BP measurement and orthostatic blood pressure test should always be done before taking any blood samples.
- Collection of blood and urine samples for safety laboratory evaluation.
- Documentation of any adverse events.
- Documentation of concomitant therapies

A patient who reverses the decision to withdraw consent should be re-consented with the latest version and will continue the visit schedule according to the date of randomisation.

Proprietary confidential information.

© 2016 Boehringer Ingelheim International GmbH or one or more of its affiliated companies. All rights reserved.

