6.7 BASELINE, TIME WINDOWS, AND CALCULATED VISITS

With regard to efficacy and safety endpoints, the term “baseline” refers to the last observed measurement prior to administration of any randomised study medication.

In general, the date and clock time of the first drug administration will be used to separate pre-treatment from on-treatment values; a notable exception to this rule is HbA_{1c} for which only the date will be used. Measurements taken after the first intake of randomised trial drug will be considered on-treatment values if they have been obtained up to end of the parameter specific follow-up period as defined in Table 6.7:1 below and will be assigned to the randomised trial drug for efficacy analyses and to the first trial drug taken for safety analyses.

Table 6.7: 1 Endpoint specific follow-up period for the assignment to active treatment

Endpoint	Last day of assignment to treatment phase (days after trial drug stop date)
Efficacy	
HbA _{1c}	7
FPG	1
Body weight	1
BP	1
HR	1
Waist circumference	7
Safety	
AEs	7
Safety laboratory measurements	3

Measurements taken after the end of the endpoint specific follow-up period and after the last intake of trial drug will be considered post-treatment values.

Table 6.7: 2 Time windows for on-treatment efficacy measurement scheduled for each on-treatment visit

Visit number	Visit label	Planned days	Time window (actual days on treatment)	
			Start	End ^A
3	Baseline	0	NA	1 ^B
4	Week 4	28	2	56
5	Week 12	84	57	105
6	Week 18	126	106	147
7	Week 24/EOT	168	148	Trial drug stop date + X days

^A In case of premature discontinuation of the trial drug a Visit 7.2 has to be performed. If such a Visit 7.2 falls into the time window of a previous visit, measurements will be assigned to this previous visit and the visit value will be determined as described below. In this case the time window for the visit that includes Visit 7.2 will end X days after the trial drug stop date, including Day X. The definition of X is endpoint specific, cf. [Table 6.7: 1](#). No time window for optional visit is planned.

^B Only values taken prior to the start of treatment with randomised trial drug will be considered baseline values. Time windows will be used for assignment of measurements to scheduled visits.

Reasons to base the time windows on the actual treatment start date rather than the randomisation date are:

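### The on-treatment window for safety laboratory values ends 3 days after the last dose, but a compliant discontinuation visit may fall on days 4 to 7, so its samples miss the creatinine-doubling table

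*SAP*

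**What the plan says.** SAP Table 6.7: 1 gives each endpoint its own follow-up period for assignment to treatment: 3 days for safety laboratory measurements, 7 days for adverse events and HbA1c, and 1 day for FPG, weight and blood pressure. SAP 7.8.2 repeats the laboratory rule: "Laboratory measurements taken up to 3 days after the last administration of randomised trial drug will be considered as on-treatment". SAP 6.7 settles what happens to anything later: "Measurements taken after the end of the endpoint specific follow-up period and after the last intake of trial drug will be considered post-treatment values". SAP 7.8.2 adds an inclusion rule: "Only patients with at least one available on-treatment value will be included in the analysis of an individual laboratory parameter".

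Protocol 6.2.3 says that for patients who stop early and agree to be followed, the premature treatment discontinuation visit "should be performed within 7 days of last intake of study drug or as soon as possible including all examinations and assessments" belonging to Visit 7.2. For those who do not wish to keep to the schedule, "Visit 7.2 should be performed within 7 days of last intake of study drug"; the same 7 days apply to patients who withdraw consent. The Flow Chart marks safety laboratory tests at the discontinuation visit. Protocol 5.2.2.2 sets the residual effect period for adverse events: "The REP is defined as ≤ 7 days following last intake of trial medication".

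**The concern.** The visit meant to capture safety data when a patient stops the drug may, within the rules, fall outside the window in which its laboratory results count. Completers are hardly touched, because no dose is given at Visit 7.2 and their last dose is normally the day before. The gap falls on patients who stop early.

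It also makes two parts of the report disagree. The renal event of special interest (Protocol 5.2.2.1, SAP 7.8.1.5) is itself a laboratory criterion: creatinine at least twice baseline and above the upper limit of normal. The summary in SAP 7.8.2 counts essentially the same finding, but only on treatment. One uses 7 days and the other 3, so a reader could see two counts of one finding with nothing to explain the difference.

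**Working it through.** No published figure is in dispute, so the check sets the rules side by side and then sizes the gap under stated assumptions.

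**1. The gap.** The laboratory window ends on day 3 (SAP Table 6.7: 1 and 7.8.2). The discontinuation visit is allowed to day 7 (Protocol 6.2.3). Uncovered: days 4 to 7, which is 7 − 3 = 4 of the 7 allowed days.

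**2. One sample traced through the plan.** Take a discontinuation sample on day 5 with creatinine doubled and above normal.
- Protocol: compliant.
- Adverse event rules (SAP 7.8.1.1, 7.8.1.5): if reported with onset that day, a treatment-emergent event of special interest.
- Laboratory rules (SAP 6.7, 7.8.2): post-treatment, so not in the on-treatment doubling summary.
- Other presentations: it appears in the individual listings. The extra 30-day presentation in SAP 7.8.2 concerns liver findings only.

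**3. What the patient keeps.** A patient who stops after Week 12 still has the Week 12 panel as an on-treatment value. Only the discontinuation result is lost. A patient with no earlier on-treatment value for a parameter leaves the analysis of that parameter.

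**4. Patients who lose the discontinuation sample.** Inputs from Protocol 7.6: 64 per arm, inflated to 77. The inflation reproduces: 64 × 1.2 = 76.8, rounded to 77; 2 × 77 = 154.
- Early stops, low: 154 − 2 × 64 = 26. High: 0.20 × 154 = 30.8, about 31.
- Share of discontinuation visits on days 4 to 7: assumed 25% to 75%, because the documents give no distribution.
- All who stop are assumed to attend the visit.
- Low: 26 × 0.25 = 6.5, about 7 patients (6.5/154 = 4.2%).
- High: 31 × 0.75 = 23.25, about 23 patients (23.25/154 = 15.1%).
- Visits spread evenly over days 1 to 7 (share 4/7): 26 × 4/7 = 14.9 and 31 × 4/7 = 17.7, so about 15 to 18 patients.

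**5. Of these, patients with no scheduled on-treatment panel.** This depends on Week 4. Protocol 5.2.3 limits that visit to FPG, but the Flow Chart marks safety laboratory tests at Visit 4. Assume stops are spread evenly over 168 days.
- Week 4 gives FPG only: stops before Week 12 are 84/168 = 1/2. 6.5/2 = 3.3 and 23.25/2 = 11.6, so about 3 to 12 patients.
- A panel is drawn at Week 4: stops before Week 4 are 28/168 = 1/6. 6.5/6 = 1.1 and 23.25/6 = 3.9, so about 1 to 4 patients.

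These are patients whose samples go uncounted, not missed abnormalities. The documents give no rate of creatinine doubling, so the number of missed events cannot be computed.

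**The case against.** The strongest reply is that 3 days is a sound choice. The windows are set by endpoint, the 7-day residual effect period is defined for adverse events, and Protocol 3.2 puts the drug's pharmacodynamic effect at about 3 days after the last dose. That stands as a reason to keep 3 days for mean changes, although the SAP does not give it as the reason.

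A second reply also stands: a 7-day window would do harm in tables built on the last on-treatment value. Protocol 1.2 reports that eGFR returned to baseline after the drug was stopped. A day 4 to 7 value could then replace a true on-drug value in a shift table and hide a change.

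Third, much is caught elsewhere. A doubling of creatinine must be reported as an event of special interest, clinically relevant laboratory changes are recorded as adverse events, liver findings run to 30 days, and all values are listed. This narrows the point without closing it. Listings give no count by arm, adverse event recording of other laboratory changes depends on the investigator's judgement, and no 7-day table exists for creatinine, electrolytes or haematology.

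Fourth, the size is soft. Flow Chart footnote S asks for the visit as soon as possible, which suggests many fall by day 3. The 20% is a sample-size allowance, not a forecast of attended discontinuation visits. Both objections hold.

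**Conclusion.** The mismatch is real and limited. Compliant samples on days 4 to 7 are left out of the on-treatment creatinine-doubling table and, where those are restricted to on-treatment values, out of the clinically-significant-abnormality tables. The range of 7 to 23 patients rests on assumed visit timing and full attendance, and prompt visits would lower it. Efficacy is unaffected and the laboratory analyses are descriptive.

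Three stronger readings are tempting, and the documents do not support them:
- A reader might infer that laboratory results of patients who stop drop out in general. Only samples after day 3 do.
- A reader might infer that abnormalities are selectively understated. No text shows that renal or electrolyte abnormalities concentrate in patients who stop, and the rule is the same in both arms.
- A reader might infer that minimum and maximum values are lost too. SAP 6.6.3 does not clearly restrict them to on-treatment values, and the abnormality tables follow an internal macro and guideline that are not reproduced in the SAP.

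**What to change.** A cheap improvement. In SAP 7.8.2, with a note to Table 6.7: 1, count the creatinine-doubling and clinically-significant-abnormality tables to 7 days after the last dose, or add a supplementary 7-day version of each. This matches the adverse event window and the discontinuation-visit window. In tables of any occurrence, a longer window can add events but cannot displace an earlier on-drug value. Keep 3 days for mean changes, last-value reference-range tables and the eGFR and eCCr shift tables.

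The cost is a sentence or two in the SAP and one or two extra tables; no new data are needed. The downside is that some day 4 to 7 values will reflect partial recovery or events arising after the drug was stopped. Discontinuation visits later than day 7 would still not be counted.
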